4.3.1. Screen Failures

- Subjects who do not meet the Inclusion/Exclusion criteria for entry into the study ("screen failures") may be rescreened one time in selected cases (with written permission from the Sponsor); for example, to meet a drug washout period.
- Subjects who do not enter the study due to administrative reasons (for example, exceeding the screening window due to issues with appointment scheduling or obtaining results of laboratory data) may be rescreened one time (with written permission from the Sponsor); this rescreening option is in addition to the rescreening permitted above.

- Neither of the rescreening options is to be used to recheck a subject who is likely unsuitable for the study, for example, to check whether their chronically abnormal laboratory test is closer to normal range.
- Subjects who are permitted to rescreen must repeat the informed consent process and sign a new form; they will receive a new subject number. In these cases, certain screening tests do not need to be repeated (per investigator judgment) if they were performed within 60 days of rescreening consent, these include: chest x-ray and QuantiFERON® TB-Gold In-Tube test

5. INVESTIGATIONAL MEDICINAL PRODUCTS

5.1. Randomization, Blinding and Treatment Codes

Subjects will be assigned a screening number at the time of consent. The Day 1 visit and randomization cannot occur until the investigator has received the results of the screening tests and subject eligibility has been confirmed. Once eligibility is confirmed, each subject will be assigned a unique subject number, which will not be reassigned to any other subject.

At the Day 1 visit, subjects will be randomized in a 1:1:1 ratio to Dosing Group 1, 2, or 3. Randomization will be stratified by disease activity at Screening: DAS28(CRP) > 5.1 or DAS28(CRP) > 3.2 and \leq 5.1. In addition, subjects will be stratified by prior use of RA biologics including the TNF inhibitor being administered during Screening (\geq 3 or $<$ 3). The IXRS will assign blinded study drug numbers at each study drug administration visit, and study drug will be dispensed to the subject in a blinded fashion until Week 12.

5.1.1. Procedures for Breaking Treatment Codes

In the event of a medical emergency where breaking the blind is required to provide medical care to the subject, the investigator may obtain treatment assignment directly from the IXRS system for that subject. Gilead recommends but does not require that the investigator contact the Gilead medical monitor before breaking the blind. Treatment assignment should remain blinded unless that knowledge is necessary to determine subject emergency medical care. The rationale for unblinding must be clearly explained in source documentation and on the case report form/ electronic case report form (CRF/eCRF), along with the date on which the treatment assignment was obtained. The investigator is requested to contact the Gilead medical monitor promptly in case of any treatment unblinding.

Blinding of study treatment is critical to the integrity of this clinical trial and therefore, if a subject's treatment assignment is disclosed to the investigator, the subject will have study treatment discontinued. All subjects will be followed until study completion unless consent to do so is specifically withdrawn by the subject.

Gilead Drug Safety and Public Health (DSPH) may independently unblind cases for expedited reporting of suspected unexpected serious adverse reactions (SUSARs).

5.2. Description and Handling of GS-5745 and Placebo

5.2.1. Formulation

GS-5745 for SC injection is formulated as a sterile, aqueous buffered solution in a single-use pre-filled syringe (PFS) with a plunger stopper. The buffered solution contains acetate at pH 5.0, sucrose and polysorbate 20 added for stabilization. Each PFS is intended to deliver 1 mL containing 150 mg GS-5745 at a concentration of 150 mg/mL.

Placebo for SC injection is formulated as a sterile, aqueous buffered solution in a single-use PFS with plunger stopper. The buffered placebo solution contains the same excipients as the GS-5745 formulation: acetate at pH 5.0, sucrose and polysorbate 20. Each PFS is intended to deliver 1 mL of buffered solution.

5.2.2. Packaging and Labeling

GS-5745 and placebo for SC injection are supplied in 1 mL type I clear single-use glass PFS with a coated elastomeric plunger stoppers.

Study drug(s) to be distributed to centers in the United States (US) and other participating countries shall be labeled to meet applicable requirements of the US Food and Drug Administration (FDA), EU Guideline to Good Manufacturing Practice – Annex 13 (Investigational Medicinal Products), and/or other local regulations.

Gilead or designated distribution depots will distribute study drug to centers as per Good Manufacturing Practice (GMP) requirements.

5.2.3. Storage and Handling

GS-5745 and placebo for SC injection are to be shipped and stored under refrigeration between 2 to 8 °C (36 to 46 °F). Storage conditions are specified on the label.

Upon arrival at the clinical center, the study drug products must be stored in a secure area, accessible only to authorized study site personnel. To ensure drug stability and proper product identification, the drug products should be stored in the kits in which they are supplied until needed.

Consideration should be given to handling, preparation, and disposal through measures that minimize drug contact with the body.

5.3. Dosage and Administration of GS-5745 and Placebo to Match

Subcutaneous injections of study drug (GS-5745/PTM) should be administered to 1 of 4 locations: to the right thigh, left thigh, right abdomen, or left abdomen (abdominal injections should be made at or below the level of the navel, avoiding the area within 5 cm [two inches] of the navel). If a subject is dosing their TNF inhibitor medication on the same day as their study drug, the subject should be instructed to inject their TNF inhibitor in a different site than the study drug. Information regarding which site was used for study drug injection will be collected throughout the study.

GS-5745 or placebo will be administered SC at the research center at Day 1 and Weeks 1, 4 and 8 during the blinded part of the study. All injections should be delivered within 1 hour of the first SC injection. The investigator or a qualified designee must be present during the administration of SC injections at Day 1 and Week 1. After training for SC injection at the study site, the subject will be allowed to administer the remaining weekly SC study drug doses at

home, except for those doses which coincide with scheduled study visits; in those cases, the study drug should be administered at the site, under direction of study staff (to enable timing for PK blood draws or other study procedures).

During the OLE portion of the study, GS-5745 will be administered SC at the research center at Weeks 12 and 13. Afterwards, subject will administer the subsequent weekly SC study drug doses at home, except for those doses which coincide with scheduled study visits; in those cases, the study drug should be administered at the site, under direction of study staff (to enable timing for PK blood draws or other study procedures).

In any part of the study, if the subject has a body temperature of $> 38^{\circ}\text{C}$ (100.4°F), or the subject feels unwell or is otherwise unfit to receive study drug at a given scheduled weekly injection, the subject should not be administered study drug. In consultation with the medical monitor, the Investigator may delay dosing until the parameters above have resolved.

If a subject fails to dose the study drug within the 3 day window of the scheduled SC weekly dose during the blinded part of the study, they should contact the study site for instructions on dosing. The investigator and the Medical Monitor will determine if a late dose of study drug is acceptable to administer or if the dose should be skipped. If a subject misses >3 of the first 12 scheduled doses of study drug, the Gilead medical monitor should be contacted to discuss if the subject should be withdrawn from the study. See below for missed doses of concomitant medications (Section 5.4.1).

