- Clinical laboratory testing, to include: Hematology, urinalysis, chemistry panel and CRP (blinded period Study Day 1, Weeks 1,

4, 12, and the 30-day follow-up), Estimated Glomerular Filtration Rate (based on MDRD study equation will be calculated week 12 , 30 day follow-up and ESDD. In the OLE hematology, urinalysis, chemistry, CRP labs will be checked every 6 weeks and at the 30-day follow-up visit , Estimated Glomerular Filtration Rate (based on MDRD study equation) will be calculated at weeks 24, 26, 28 and 60 and the ESDD .

- Subjects with positive HBV Core Ab and/or HCV Ab during screening are to have the respective DNA or RNA PCR test every 3 months during the study. A positive test for hepatitis virus should lead to study discontinuation as per Section 3.5.2
- Serum β -HCG pregnancy test (at Week 12 and at the 30-day follow-up and ESDD), and urine pregnancy tests (at Day 1 and every 4 weeks) in women of child-bearing potential. For urine pregnancy tests performed at home, the site will contact the subject to confirm the urine pregnancy test was performed and will document the result as per protocol. Subjects may also present to the site for the urine pregnancy testing if they prefer.
- In the blinded period, questionnaires and disease activity measures will be administered at Day 1, Weeks 1, 4, 8, 12, ESDD and at the 30-day follow-up visit. In the OLE, these assessments will be performed every 12 weeks, at Week 64, ESDD and at the 30-day follow-up visit.

Study Drug Administration:

Blinded Period

SC study drug administration will occur at the study site on Day 1, Weeks 1, 4, and 8. Subjects will remain at the study site for at least 30 minutes after the first 2 injections of study drug for observation. This time may be extended per judgment of the investigator. After receiving SC instruction at the study site during the first 2 study drug injections, subjects (or their caretakers) who are judged capable, will be allowed to self-administer SC injections at home during the weeks where on-site visits are not scheduled.

Open Label Extension (OLE)

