Subjects who permanently discontinue study medication for any reason are to receive standard of care treatment for their RA as determined by the investigator, and those subjects should be encouraged to continue study visits and procedures, if deemed medically appropriate by the investigator. Subjects who permanently discontinue study medication for pregnancy should not continue in the study; if there are any questions regarding permanent discontinuation, these should be discussed with the Sponsor.

Subjects withdrawing from the study should complete the ESDD and 30-day follow-up visits.

Subjects are free to withdraw from the study at any time without providing reason(s) for withdrawal and without prejudice to further treatment. The reason(s) for withdrawal will be documented in the electronic case report form (eCRF).

Reasonable efforts will be made to contact subjects who are lost to follow-up. These must be documented in the subject's file.

The sponsor has the right to terminate the study at any time in case of safety concerns or if special circumstances concerning the study medication or the company itself occur, making further treatment of subjects impossible. In this event, the investigator(s) and relevant authorities will be informed of the reason for study termination.

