5.4.1. Missed Doses of Concomitant Medications (TNF and MTX)

- TNF inhibitor:

If a subject fails to dose their SC TNF inhibitor within +3 days (for weekly TNF inhibitors), +5 days (for biweekly TNF inhibitors) or +9 days (for monthly TNF inhibitors), of their scheduled TNF inhibitor dose date during the blinded part of the study, they should contact the study site for instructions on dosing. The investigator will determine if a late dose of TNF inhibitor should be administered, or if the dose should be skipped. If the site determines (per concomitant medication reporting) that a subject has missed $>25\%$ of their TNF inhibitor doses, the Gilead medical monitor should be contacted to discuss whether the subject should be withdrawn from study drug.

- Methotrexate:

If a subject fails to dose their weekly MTX within +3 days of their scheduled MTX dose date during the blinded part of the study, they should contact the study site for instructions on dosing. The investigator will determine if a late dose of MTX should be administered, or if the dose should be skipped. If the site determines (per concomitant medication reporting) that a subject has missed >25% of their MTX doses, the Gilead medical monitor should be contacted to discuss whether the subject should be withdrawn from study drug.

5.4.2. Allowed Concomitant Medications:

- Antimalarials (hydroxychloroquine, chloroquine): Are allowed provided that the subject is on a stable prescription for at least 4 weeks prior to the first dose of study drug. This stable dose should be maintained through Week 12; dosing of these medications may be adjusted by the investigator after the Week 12 visit is complete. If these medications are to be discontinued, they should be discontinued at least 4 weeks prior to the first dose of study drug.
- Chronic NSAIDs/COX-2 inhibitors, opioids, tramadol, and acetaminophen/paracetamol: Are allowed provided that the subject is on a stable prescription for at least 4 weeks prior to the first dose of study drug. This stable dose should be maintained through Week 12; dosing of these medications may be adjusted by the investigator after the Week 12 visit is complete. If these medications are to be discontinued, they should be discontinued at least 2 weeks prior to the first dose of study drug.

NOTE: All analgesics (including chronic NSAIDs) should be held on the day of study visits, until after all study procedures for that day have been completed, as much as possible.

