6.3. Blinded Treatment Assessments (Week 1 through Week 12)

All visit tests and procedures should be completed as indicated in [Appendix 2](#). Joint counts, patient global assessment of pain, physician's assessment of global disease activity, patient's

assessment of physical function, SF-36, HAD-QI should be administered prior to lab draws and study drug administration, as much as possible.

On-Treatment Assessments

- Concomitant medications
- Vital signs
- CPE at Week 12 and at ESDD if not done in the prior 12 weeks
- Targeted Physical exam (TPE) at all other visits
- 12 lead ECG at Week 12 and ESDD if not done in the prior 12 weeks
- hsCRP
- ESR
- urinalysis
- Clinical laboratory tests: hematology, chemistry panel on Study Day 1, Weeks 1, 4, 12, and at the 30-day safety follow-up (if applicable)
- Serum β -HCG (Week 12 and 30-day follow-up and ESDD), and urine pregnancy tests on Day 1 and every 4 weeks in women of childbearing potential.
- Subject questionnaires and disease activity measures will be administered at Day 1, Weeks 1, 4, 8 and 12, ESDD and 30-day follow-up (if applicable)
- Subjects with positive HBV Core Ab and/or HCV Ab during Screening should have the respective DNA or RNA PCR test for viral load every 3 months during the study; a positive test for hepatitis virus should lead to study discontinuation as per Section 3.5.2.
- Estimated glomerular filtration rate (eGFR) based on MDRD at week 12, 30 day follow-up and ESDD (calculated at central lab)

Pharmacokinetics/pharmacodynamics:

PK blood draws: PK blood draws will be done prior to dosing at Weeks 1, 4 and 8, anytime on Week 12 and at ESDD (if applicable)

Optional PK Sub-study: PPD

GS-5745 Anti-Drug Antibodies (ADA): Blood draws for ADAs will be done prior to dosing on Study Day 1, Weeks 4 and 8, anytime at Week 12 and the 30-day follow-up visit of the blinded period.

Biomarker Blood Draws: Blood biomarkers will be collected at Day 1, Weeks 4 and 12 in the blinded period of the study. In the OLE biomarker samples will be collected every 3 months starting at week 24.

Genomic Testing

Optional Genomic Testing: **PPD**

Description of Selected Assessments

Physical Exam

A CPE is required at Screening, Week 12 of the blinded period, and Week 64 of the OLE. A TPE will be performed at other study visits. A limited physical exam is defined as an examination driven by subject signs/symptoms and/or adverse events. Height is captured at screening only.

Vital Signs

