If a subject discontinues study dosing (for example, as a result of an AE or needed for prohibited medication), every attempt should be made to keep the subject in the study and to perform the required study-related follow-up and procedures (see Section 3.5, Criteria for Discontinuation of Study Treatment) as long as it is medically appropriate for the subject to continue. If this is not possible or acceptable to the subject or investigator, the subject may be withdrawn from the study and will be asked to return for the Early Study Drug Discontinuation (ESDD) visit. These subjects will not be eligible for the OLE.

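### Protocol Section 5.3 raises withdrawal from the study for missed doses where Sections 3.5.2, 5.4.1 and 6.5 stop study drug only and keep visits, so some Week 12 DAS28(CRP) values may be lost

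*Protocol*

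**What the plan says.** **Missed study drug.** Protocol Section 5.3 sets the trigger: "If a subject misses >3 of the first 12 scheduled doses of study drug". The consequence is that "the Gilead medical monitor should be contacted to discuss if the subject should be withdrawn from the study".

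**Missed TNF inhibitor or methotrexate.** Section 5.4.1 uses a parallel sentence when more than 25% of doses are missed, but with a different object: "the Gilead medical monitor should be contacted to discuss whether the subject should be withdrawn from study drug".

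**General rule.** Section 3.5.2 lists the grounds for permanently stopping study medication. Noncompliance, HBV DNA positivity and HCV RNA positivity are among them. Of subjects who stop for any reason it says "those subjects should be encouraged to continue study visits and procedures, if deemed medically appropriate by the investigator"; pregnancy is the only stated exception. Section 6.5 says that after dosing stops "every attempt should be made to keep the subject in the study", with withdrawal only where that is not possible or acceptable.

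**Positive hepatitis test.** Section 6.3 says "a positive test for hepatitis virus should lead to study discontinuation as per Section 3.5.2". The Synopsis and Section 6.4 say the same. Exclusion criterion 12 (j and k) cites the same Section 3.5.2 for stopping study drug.

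**The concern.** Stopping study drug and leaving the study are different actions in this protocol. A subject who stops drug is asked to keep attending. A subject who withdraws is asked for an early discontinuation (ESDD) visit and a 30-day follow-up visit, and the remaining scheduled visits fall away. For missed study-drug doses, Section 5.3 points to the second path and Sections 3.5.2 and 6.5 to the first.

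The efficacy set is everyone randomised and dosed (Protocol Section 8.2.1.1), so non-adherent subjects belong in the primary comparison. Missing four doses happens after randomisation and may reflect tolerability or lack of effect. If those subjects leave, their Week 12 values are absent for a reason that may be related to treatment. The planned MMRM (Protocol Section 8.5) is valid when data are missing at random, and selective withdrawal strains that assumption. Each lost value also uses up a sample size with little margin.

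**Working it through.** **1. The instructions side by side**

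| Event | Ends study participation | Stops study drug only |
|---|---|---|
| Missed study drug | 5.3 (for discussion) | 3.5.2 (noncompliance), with visits continuing under 3.5.2 and 6.5 |
| Missed TNF inhibitor or MTX | none | 5.4.1 (for discussion) |
| Positive hepatitis test | Synopsis, 6.3, 6.4 (each citing 3.5.2) | 3.5.2; exclusion criterion 12 j and k |

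The hepatitis entries on the left cite Section 3.5.2 for something it does not say.

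**2. When a missed-dose withdrawal would cost the Week 12 value**

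- The twelve weekly doses fall on Day 1 + 7k, for k = 0 to 11: Days 1, 8, 15, 22, 29, ..., 78.
- If the Day 1 dose is given, the earliest fourth miss is the fifth dose: 1 + 7 × 4 = Day 29, or Day 32 after the 3-day window in Section 5.3.
- SAP Table 3-1 assigns Days 19 to 43 to Week 4, Days 44 to 71 to Week 8, and Day 72 onward to Week 12.
- An ESDD visit around Day 32 therefore counts as Week 4, and Week 12 is missing. An ESDD visit on Day 72 or later counts as Week 12.
- SAP Section 3.8.2 summarises the 30-day follow-up as a separate visit, so it does not fill the gap. SAP Section 6.2.1 does not impute missing DAS28(CRP) components.

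**3. When a positive hepatitis test would cost it**

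The blinded-period schedule (Protocol Appendix 2) marks the hepatitis row at Screening and Week 12 only. The first scheduled on-study result thus comes from the visit at which Week 12 DAS28(CRP) is measured.

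**4. Planned power**

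Inputs (Protocol Section 8.9, SAP Section 1.3): difference 1.2, SD 1.35, two-sided α 0.05, 25 per arm, 15% dropout.

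- Standardised difference: d = 1.2 / 1.35 = 0.889.
- Two-sample t-test power comes from the noncentral t distribution with noncentrality d × √(n/2) and 2n − 2 degrees of freedom.
- The plan's figure reproduces: 21 evaluable per arm are needed for 80%, and 21 / 0.85 = 24.7, rounded up to 25.

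| Evaluable per arm | Lost of 25 | Noncentrality | Power |
|---|---|---|---|
| 21 | 4 (16%) | 2.880 | 80.3% |
| 20 | 5 (20%) | 2.811 | 78.2% |
| 19 | 6 (24%) | 2.740 | 76.0% |
| 18 | 7 (28%) | 2.667 | 73.6% |

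The last three rows are assumed scenarios. The documents give no missed-dose rate, and the t-test takes no credit for the earlier visits that an MMRM would use.

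**The case against.** Several stronger conclusions are tempting, and the documents do not support them.

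- **That missed doses mean withdrawal.** Section 5.3 requires only a discussion with the medical monitor. Retention is the protocol's stated policy in Sections 3.5.2 and 6.5, so the monitor may well keep the subject in. Loss of data is a risk, not a certainty.
- **That a positive hepatitis test costs Week 12 data.** On the schedule it normally cannot; only an unscheduled or earlier test could. Section 6.4 covers the extension, after the primary endpoint. Because the hepatitis sentences defer to Section 3.5.2, they can also be read as loose wording that points to the right rule.
- **That every withdrawal loses the endpoint.** The ESDD visit includes joint counts, hsCRP and the disease questionnaires, and from Day 72 it counts as Week 12. For earlier withdrawals the MMRM would still use whatever was observed at Weeks 1, 4 and 8.
- **That power falls by the amounts shown.** The 15% allowance may already cover some or all of these losses.
- **That the reported results are biased.** The trial stopped after 15 subjects (SAP Section 1.3) and no hypotheses are tested (SAP Section 6.2.2). The effect there is limited to missing values in descriptive summaries.

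All five limits stand. What survives is that Section 5.3 puts a different action up for discussion than Sections 3.5.2 and 6.5 provide for, and that following it before Day 72 would remove a primary-endpoint value.

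**Conclusion.** The inconsistency is real and worth correcting, but its consequence is conditional. For missed study drug, a site following Section 5.3 may lose Week 12 DAS28(CRP) for subjects withdrawn between about Day 29 and Day 71. Any bias in the planned comparison has unknown direction and cannot be sized from the documents. The power cost is about 2 percentage points for the first loss per arm beyond the allowance and 6.7 points for three (80.3 − 73.6), if such losses occur and are additional to the 15%.

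The hepatitis wording is a separate and smaller conflict, chiefly about follow-up in the open-label extension. Both matter for the design as planned; neither changes an inference, because the current SAP makes none.

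**What to change.** Reconcile the Synopsis and Sections 5.3, 6.3 and 6.4 with Sections 3.5.2, 5.4.1, 6.5 and exclusion criterion 12. The text should state that a decision to stop study drug does not in itself end study visits, and that Week 12 assessments are still sought. It should keep the limits already in Section 3.5.2: the pregnancy exception, medical appropriateness as judged by the investigator, and the subject's freedom to withdraw. When study drug is stopped remains as the sponsor sets it.

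The cost is a few words in four places, with no added visits. For the 15 subjects enrolled, the disposition summary in SAP Section 4.1 already reports study-drug completion and study completion separately, with reasons. Anyone withdrawn from the study for noncompliance can be noted from there in the report.
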